Fig. 1. Serum glucose response to HMS (closed circles) versus MAL (open circles) before and after cycling bouts (A) and area under the curve analysis for different time ranges (B). Values are expressed as mean  $\pm$  SE. (A) Intervals between time points spanned 15-min periods. a, Fasting blood before first drink ingestion (1 g/kg of body mass); b, onset of cycling bout; c, blood before time to exhaustion; d, blood immediately after time to exhaustion; e, blood 15 min after second drink ingestion (1 g/kg of body mass). (B) Between-trial values were compared using paired-samples t tests. Significant differences between trials ( $P \le 0.05$ ) are italicized. HMS, hydrothermally modified starch; MAL, maltodextrin; PreEx + Ex, before exercise plus exercise.

[figure not shown]

Fig. 4. Serum insulin response to HMS (closed circles) versus MAL (open circles) before and after cycling bouts (A) and area under the curve analysis for different time ranges (B). Values are expressed as mean  $\pm$  SE. (A) Intervals between time points spanned 15-min periods. a, Fasting blood before first drink ingestion (1 g/kg of body mass); b, onset of cycling bout; c, blood before time to exhaustion; d, blood immediately after time to exhaustion; e, blood 15 min after second drink ingestion (1 g/kg of body mass). (B) Between-trial values were compared using paired-samples t tests. Significant differences between trials ( $P \le 0.05$ ) are italicized. HMS, hydrothermally modified starch; MAL, maltodextrin; PreEx + Ex, before exercise plus exercise.

Preload®, the pre-operative carbohydrate drink used in ERP across the NHS and in our institution, has an osmolality of 135mOsm/kg when mixed in the standard dilution (one 50g sachet is diluted with 400ml water). Generation UCAN is a powder-based sports energy drink mix, which makes use of SuperStarch, which has an osmolality of 89mOsm/kg when 60g, is diluted into 500ml water. This indicates that Generation UCAN will be emptied from the stomach more rapidly than Preload®.

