# 5.3 Interventions

Following consent and randomisation at the Preoperative Assessment Clinic (POAC) visit one group will receive the current pre-operative carbohydrate solution, *Preload*® (a maltodextrin solution), and the other group will receive *Generation UCAN* (a hydrothermally modified starch solution) to take home.

In both cases these will be dispensed as a powder in a clear plastic zip lock bag to ensure blinding of the patient (the research team will have decanted the appropriate dose of each supplement into these bags and will be aware of the allocated intervention). This will be a single sachet, in the case of *Preload®*, and an equivalent weighed and measured volume from a large tub, in the case of Generation UCAN. Both groups will be instructed to reconstitute the powder provided in 400mls of water on the day of surgery, and consume it between two and three hours before surgery, as per standard practice in the ERP.

Both groups will also be instructed to consume approximately 500mls (1 pint) of water with their evening meal the evening before surgery to remain well hydrated.

The Control group will receive 47.5g of carbohydrate in the form of Preload®.

The Intervention group will receive 56.55g of flavoured Generation UCAN (providing 47.5g of carbohydrate).

All other aspects of patient care will be standardized as per our ERP (see Appendices).

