#### **SECONDARY OUTCOMES**

- Change in insulin resistance from baseline on POD 2 and POD 3 measured using a technique called HOMA, which utilises serial fasting blood glucose and insulin measurements.
- Stress response following surgery, measured by sampling cortisol levels preoperatively, at the end of surgery, and at 24 hours post-operatively and the inflammatory response measured by CRP levels preoperatively, and on POD 1,2 and 3.
- Ultrasound measurement of gastric volume pre-operatively (see Appendices for technique)
- Recovery profile including:
  - PQRS (see Appendices) score measured pre-operatively, at 2 hours after surgery, POD 3 and POD 7;
  - Muscle strength measured using a grip strength dynamometer pre-operatively, twice daily (morning and afternoon) on POD 1, 2 and 3, and then once daily on alternate days thereafter until discharge (the patient's dominant hand will be used for this measurement, and the best out of three consecutive strengths will be used with mean values analysed);
  - Time to surgical fitness for discharge (see Appendices for criteria) measured in hours (date and time of fitness for surgical discharge is recorded in the ERP database).
- Morbidity measured using the POMS score on POD 2 and POD 5 (see Appendices).
- PONV VAS score on POD 1.
- Sensations of thirst & hunger VAS score immediately pre-operatively and on POD 1.
- Caloric intake POD 1 and 2.
- Ambulation time POD 1 and 2.
- Adverse events i.e. aspiration and hypo- or hyperglycaemia (these are the only relevant safety assessments for these interventions) will be assessed on the operative day for the former & up to the end of POD 1 for the latter.
- Cost analysis: difference in cost between doses of Pre-Load & Generation UCAN and costs of respective hospital and critical care lengths of stay.

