#### **OPERATIVE DAY PRE-SURGERY**

- Confirm allocated drinks consumed as per instructions & document
- · Thirst and hunger sensation VAS score
- Blood samples on morning of surgery fasted (before consuming the intervention) if not done in POAC.
  - Fasting Glucose
  - Fasting Insulin (3 sample to be taken at 5 minute intervals)
  - Cortisol
  - o CRP
  - HbA1c (if not recently measured)
- Duration surgery (obtained from Theatreman system)
- Volume of blood loss
- Description of operation and type of primary analgesia obtained from Theatreman system or ERP Database
- Calories consumed

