## METHODS FOR ANY ADDITIONAL ANALYSES (EG, SUBGROUP AND ADJUSTED ANALYSES)

If differences are observed in baseline demographic and/or clinical variables prognostic of outcome, then the analysis of the primary and secondary outcomes will be adjusted for using regression-based analysis appropriate to the type of outcome variable. The trial statistician will describe details of sub-group analysis in the statistical analysis plan if possible.

DEFINITION OF ANALYSIS POPULATION RELATING TO PROTOCOL NON-ADHERENCE (E.G., AS RANDOMISED ANALYSIS), AND ANY STATISTICAL METHODS TO HANDLE MISSING DATA (EG, MULTIPLE IMPUTATION) All analysis will be performed according to the intention to treat principle. The primary analysis will be based only on data obtained; sensitivity analysis will explore sensitivity to assumptions around missing data and details will be included in the statistical analysis plan devised by the trial statistician.

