#### 8.2 HARMS

#### ADVERSE EVENTS (AE)

Any untoward medical occurrence or effect in a patient treated with the trial protocol, which does not necessarily have a causal relationship with trial treatment. An adverse event (AE) can therefore be any

unfavourable symptom or disease temporarily associated with the trial treatment, whether or not it is related to the trial treatment.

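### The intention-to-treat rule for all analyses also covers aspiration and glycaemic events, so patients who never took the drink stay in the harm denominators; a by-drink-consumed safety summary should be added

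*Protocol*

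**What the plan says.** Section 7.3 of the protocol, under the sub-heading on the analysis population and non-adherence, sets one rule: "All analysis will be performed according to the intention to treat principle". The next sentence, "The primary analysis will be based only on data obtained", deals with missing values. It does not remove a patient who skipped the drink but has outcome data. What this part of section 7.3 leaves to the statistical analysis plan is subgroup and missing-data detail, not the choice of population.

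The harms are secondary outcomes in section 5.4: "Adverse events i.e. aspiration and hypo- or hyperglycaemia (these are the only relevant safety assessments for these interventions". Gastric volume is a separate item in the same list: "Ultrasound measurement of gastric volume pre-operatively (see Appendices for technique".

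Under section 5.3 patients take the powder home, mix it themselves and are told to "consume it between two and three hours before surgery, as per standard practice in the ERP". On the day of surgery, section 7.1 tells staff to "Confirm allocated drinks consumed as per instructions & document".

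Section 8.2 defines an adverse event by exposure: "Any untoward medical occurrence or effect in a patient treated with the trial protocol". Its reporting procedures start the recording period at treatment, not at randomisation.

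**The concern.** Aspiration and glycaemic disturbance matter here as possible effects of drinking a carbohydrate solution shortly before anaesthesia. A patient who did not drink cannot have an event caused by the drink, yet under the blanket rule counts in that arm's denominator. For an efficacy claim in a superiority trial this dilution is the accepted, conservative choice. For harm it works the other way, since a real difference looks smaller than it is among those exposed.

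The protocol is also not aligned with itself. Its harms section counts from treatment and its analysis rule counts from randomisation. The intake record that would connect the two is collected, but the analysis section gives it no use.

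**Working it through.** **Inputs from the protocol.** 20 patients per group, from a difference of 15%, a standard deviation of 16%, 80% power, two-sided 5% and 10% attrition (section 5.6); 1:1 superiority design (section 4.3); chi-square test for categorical secondary outcomes (section 7.3). The protocol states no rate of non-intake and no event rate, so those below are assumptions.

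**The plan's own figure.** n = 2 × (1.960 + 0.842)² × 16² / 15² = 17.9, so 18 per group; 18 / 0.9 = 20. The stated number reproduces under the normal approximation. It is used here only as the arm size.

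**Dilution, equal non-intake.** Let f be the share not drinking in each arm, p_T and p_C the event rates among drinkers of the test and control drinks, and p_0 the rate among non-drinkers.

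- Test arm as randomised: (1 − f) p_T + f p_0
- Control arm as randomised: (1 − f) p_C + f p_0
- Difference: (1 − f)(p_T − p_C)

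The difference keeps 95%, 90% or 80% of its size at f = 5%, 10% or 20%.

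**Dilution, unequal non-intake.** The difference becomes (1 − f_T)(p_T − p_0) − (1 − f_C)(p_C − p_0). Suppose the drinks are equally harmful, p_T = p_C = 30%, with p_0 = 10%. With f_T = 20% and f_C = 0 the as-randomised difference is 0.8 × 20 − 20 = −4 points. With the shares exchanged it is +4 points. So the bias is reliably towards zero only if intake is similar in the two arms.

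**Effect on power.** Power of Fisher's exact test by full enumeration, taking p_0 = p_C. As-randomised uses 20 per arm; drinkers only uses 19, 18 or 16 per arm.

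| Assumed event rates | f | As-randomised difference | Power, as randomised | Power, drinkers only |
|---|---|---|---|---|
| 10% v 30% | 0 | 20 points | 24.2% | 24.2% |
| 10% v 30% | 5% | 19 points | 22.0% | 22.3% |
| 10% v 30% | 10% | 18 points | 20.0% | 20.5% |
| 10% v 30% | 20% | 16 points | 16.1% | 16.8% |
| 10% v 50% | 0 | 40 points | 74.2% | 74.2% |
| 10% v 50% | 5% | 38 points | 69.7% | 70.9% |
| 10% v 50% | 10% | 36 points | 64.9% | 66.8% |
| 10% v 50% | 20% | 32 points | 54.5% | 58.1% |

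For the moderate harm, restricting to drinkers gains less than one percentage point of power. The larger difference takes it to at most 3.6 points. What changes is mainly the estimate, not the chance of detecting harm.

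**The case against.** Several objections stand, and they limit the point.

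- **Size.** No non-intake rate is given. The drink timing is routine in the recovery programme and intake is checked on the day, so nearly everyone may drink. In that case the dilution is negligible.
- **Arm size.** Twenty per arm limits any statement about harm far more than the choice of population does.
- **The analysis plan.** A supporting table by exposure is ordinary content for a statistical analysis plan, which is not shown. This is only a partial answer: the protocol fixes the population for every analysis and does not defer that choice, so its sentence would need rewording to fit.
- **The harms section.** Its wording already ties adverse events to treatment. It governs what is recorded, though, and sets no denominator.

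Two stronger readings are tempting, and the documents do not support them.

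A reader might infer that gastric volume is also biased towards making the new drink look safe. Section 5.4 lists it apart from the safety assessments, and section 4.1 states an expected advantage: "This indicates that Generation UCAN will be emptied from the stomach more rapidly than Preload". For that claim intention to treat is the right default. Section 4.1 also says that carbohydrate drinks leave residual volume not significantly different from, or lower than, that after fasting. A non-drinker's stomach therefore need not make the new drink look better. Appendix 10.8 does discuss antral area and volume as markers of reflux and aspiration risk, which justifies a sensitivity analysis and no more.

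A reader might also infer that an upper limit on the harm rate is understated. With no events, the exact two-sided 95% limit, 1 − 0.025^(1/n), is 16.8% for 20 patients, 18.5% for 18 and 20.6% for 16. The arithmetic is right, but the protocol plans no single-arm limit, safety margin or non-inferiority claim. It plans a between-group test.

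**Conclusion.** The point holds in a limited form. The rule, as worded, keeps non-drinkers in the comparison of aspiration and glycaemic events, and the protocol names no exposure-based alternative although it records exposure. A drink-caused difference in event rates is reduced to (1 − f) of its size: 90% at an assumed 10% non-intake, 80% at 20%. This rests on similar non-intake in both arms and on a share that the protocol does not state. The primary outcome, the sample size and the intention-to-treat analysis of efficacy are unaffected. It is a minor improvement to the wording, not a flaw that threatens the trial's conclusions.

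**What to change.** Reword the population sentence in section 7.3 to say three things:

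1. Efficacy outcomes, including gastric volume, are analysed by intention to treat.
2. Aspiration and glycaemic events are reported by the drink actually consumed, using the operative-day intake record, with the as-randomised result beside it. Patients who drank nothing are listed separately by arm, so that any imbalance in intake is visible.
3. If wanted, a drinkers-only sensitivity analysis of gastric volume is added, labelled as such.

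How partial intake is classed for this summary should be fixed before the data are examined.

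The cost is a few lines of text and one extra table; no new data are needed. The drawback is that patients who drank are not a strictly randomised comparison, because the reasons for not drinking may be related to outcome. Showing both results meets that.

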## 8. Methods: Monitoring

#### 8.1 Data monitoring

As this is a non-CTIMP study measuring low risk interventions (nutritional supplements) a DMEC is not required. The trial will be stopped by the CI following any SAE deemed to be definitely or probably related to the new study intervention (the control arm is already standard clinical practice), however this is extremely unlikely given the nature of the intervention.

#### 8.2 HARMS

#### ADVERSE EVENTS (AE)

Any untoward medical occurrence or effect in a patient treated with the trial protocol, which does not necessarily have a causal relationship with trial treatment. An adverse event (AE) can therefore be any

unfavourable symptom or disease temporarily associated with the trial treatment, whether or not it is related to the trial treatment.

## SERIOUS ADVERSE EVENT (SAE)

An AE that:

- Results in death
- Is life-threatening
- Requires in-patient hospitalisation or prolongs existing hospitalisation
- Results in persistent or significant disability/incapacity
- Is otherwise considered to be medically significant by the investigator

## REPORTING PROCEDURES

All patients undergoing this trial are having major abdominal surgery and there is a recognised high risk of morbidity, therefore they are at risk of frequent AE. These events are largely as a result of a patient's medical condition and consequences of major surgery and may not be related to the trial. Consequently any AEs occurring as a result of patient's condition will not be reported. All other AEs that occur during the trial period from treatment to hospital discharge must be recorded in the patient notes. Any AE will be reported to the CI directly. The CI will facilitate any local monitoring by the R&D quality manager, REC review and provide access to source data as required. Following any monitoring a report will be provided which will summarise the visit and documents, along with any findings. The CI will be responsible for ensuring that all findings are addressed appropriately. Additional monitoring will be scheduled where there is evidence of suspicion of non-compliance with the Trial protocol.

#### NOTIFYING THE REC

Any SAE causally attributed to the trial interventions will be reported to the REC by the CI in an expedited fashion. AEs that do not require expedited reporting will be reported in the annual progress report, which will be submitted by the CI to the REC annually. This will commence one year from the date of approval for the trial.

## 8.3 AUDITING

The R&D Quality Manager will audit the first patients recruited. The CI will facilitate any local monitoring by the R&D Quality Manager, REC review, audits and regulatory inspections, by providing direct access to source data/documents as required. Trial participants will be informed of this during the informed consent process.

Following any monitoring, a report will be provided which will summarise the visit and the documents reviewed, along with any findings. The CI will be responsible for ensuring that all findings are addressed appropriately.

## 9. ETHICS AND DISSEMINATION

## 9.1Research ethics approval

The SuperStarch Study will be conducted in accordance with the approved Trial Protocol, ICH GCP guidelines, the Data Protection Act 1998, the Mental Capacity Act 2005, and the Medical Research Council's (MRC) Guidelines for Good Research Practice, Guidelines for Good Clinical Practice in Clinical Trials and Procedure for Inquiring into Allegations of Scientific Misconduct. The ELHT R&D Department has developed its own policies and procedures, based on these MRC guidelines, for the conduct of all its research activities. Policies regarding alleged scientific misconduct and breach of confidentiality are reinforced by disciplinary procedures.

The trial has received a favorable opinion from the <<REC name to be inserted>> REC. The CI will submit annual progress reports.

The SuperStarch Study will only be conducted once all necessary local approvals for the trial have been obtained.

## 9.2 PROTOCOL AMENDMENTS

Any important protocol modifications will not be implemented until a protocol amendment application is approved by the REC.

## 9.3 Consent

Once the research team are informed about an eligible patient as described in the recruitment section they will meet them at their next hospital attendance & provide them with a written Patient Information Sheet (PIS) and a verbal description of the study along with contact numbers should they wish further information or clarification. They will be followed by telephone in the interim to gauge interest, and again at their preoperative assessment clinical visit to ascertain if they wish to participate. Some patients may be encountered for the first time at this clinic and may be willing to participate after sufficient time to absorb the PIS, which will vary individually. If so, consent will be taken followed by randomisation in order to provide them with their allocated bags of *PreLoad®* or *Generation UCAN* to take home with them to take as directed in the intervention section.

No other aspect of care will be altered apart from that detailed in the study protocol (i.e. provision of different pre-operative drink in intervention arm). The conduct of anaesthesia and planned surgical technique will be at the discretion of the responsible clinicians.

#### WITHDRAWAL OF A PATIENT

In consenting to the trial, patients are consenting to the trial intervention they are allocated, assessments, and data collection. However, patients can withdraw from the SuperStarch Study at any time during the trial. If a patient explicitly states that they no longer wish to take part or contribute further data to the trial, their decision must be respected. The patient's withdrawal from the trial should be recorded in the patient's medical notes and no further data collected. All data collected up to the point of withdrawal will be included in the trial analysis. However, if a patient withdraws consent for any of their data to be used, these will be confidentially destroyed immediately. If a patient is randomised and later found to be ineligible, or the responsible clinician feels that it is no longer appropriate for the patient to continue taking part, then they will be withdrawn from the study and the reason for withdrawal indicated in the medical notes. Patients withdrawn will not be replaced.

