## POST-OPERATIVE DATA COLLECTION

- POSSUM score from ERP Database
- Blood samples:
  - Fasting insulin (3 samples to be taken at 5 minute intervals and glucose on the morning of POD 1, 2 and 3
  - Cortisol (at end of operation and at 24 hours)
  - o CRP (POD 1 and 3)
- PQRS score Theatre Recovery, POD 3 and POD 7.
- PONV and Thirst and hunger sensation VAS scores on POD 1.
- POMS score on POD 2 and 5
- Hand grip strength measurement twice daily on POD 1, 2 & 3 and then alternate days until discharge
- Calories intake POD1 and POD2
- Ambulation time (minutes) POD1 and POD2
- MUAC POD5 or Day of Discharge if earlier
- Adverse Events up to end POD 1.
- Date and time reached surgical fitness for discharge and actual discharge obtained from ERP Database

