## 7.2 DATA MANAGEMENT

Identifiable data including full name, date of birth and hospital number will be required by the research team for identification purposes during the post-operative phase. All patient confidentiality will be ensured. The trial team will not disclose or reproduce any information by which patients could be identified. All patient data collected will be entered on to a password-protected Microsoft Excell Spreadsheet. The CI will ultimately be responsible for data collection, quality and recording and handling however data collection will be delegated to the Clinical Research Anaesthetic Fellow and ERP Data Clerk. The R&D Quality Manager will undertake monitoring to assess data quality. A separate and secure log will be kept with consent form and identifiers to allow patient follow up. During the conduct of the trial all electronic patient data will be encrypted and all trial documents stored securely at East Lancashire Hospitals NHS Trust. Following completion of the trial all non-essential confidential documents will be destroyed and essential documents (paper and electronic) will be archived and retained securely for five years in accordance with ICH GCP guidelines. Essential documents are

those which enable both the conduct of the trial and the quality of the data produced to be evaluated and to show whether the unit complied with the principles of ICH GCP and other applicable regulatory requirements.

All archived documents should be available for inspection by appropriate authorities upon request.

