#### 9.4 CONFIDENTIALITY

Identifiable patient data, including full name, full postal address, date of birth and NHS number will be required by the CI and research team to maintain a screening and enrolment log and ensure follow up for detection of AE. This information will be kept together with all copies of consent forms in the Master Site File securely in the R&D Department. The trial team will not disclose or reproduce any information by which patients could be identified. Data will be entered and stored securely on a ELHT drive folder, with only the research team having access, within the SuperStarch Study excel spreadsheet, which will be password protected by the research team.

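### The withdrawal rule treats leaving the study and refusing further data as one event, so outcomes still available from routine records are lost and adverse-event duties after withdrawal are left unreconciled

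*Protocol*

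**What the plan says.** The withdrawal paragraph in section 9.3 first lists three things that consent covers: the allocated intervention, the assessments and the data collection. It then sets one trigger: "If a patient explicitly states that they no longer wish to take part or contribute further data to the trial, their decision must be respected". One consequence follows: the withdrawal goes into the patient's "medical notes and no further data collected". What was collected before withdrawal stays in the analysis, and withdrawn patients are not replaced. Destruction is a separate step. If the patient also withdraws consent to the use of their data, "these will be confidentially destroyed immediately".

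Other sections bear on this:

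- **Section 7.1** names the patient notes and the ERP Database as data sources. Its post-operative list includes "Date and time reached surgical fitness for discharge and actual discharge obtained from ERP Database".
- **Section 7.3** applies intention to treat to all analyses and bases the primary analysis on the data obtained.
- **Section 8.2, Reporting procedures,** leaves out events due to the patient's condition and then says: "All other AEs that occur during the trial period from treatment to hospital discharge must be recorded in the patient notes". Any adverse event is also to go directly to the CI.
- **Section 9.4** says identifiers are held partly to "ensure follow up for detection of AE".
- **Section 7.2** says essential documents are "archived and retained securely for five years".

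**The concern.** Consent is described as having three parts, but withdrawal has only one level. A patient who has taken the drink and has had enough of blood samples, questionnaires and grip tests may say that they want to leave the study and yet have no objection to staff reading a discharge time from a database. The rule gives that patient no such option. Data that were never collected cannot be restored later by any analysis plan, so this has to be settled in the protocol and the consent documents.

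Two things are at stake. The first is the completeness of the recovery outcomes that are supposed to be analysed as randomised. The second is clarity on safety. Section 8.1 provides no DMEC and makes one SAE judged definitely or probably related to the new intervention decisive for the trial. Staff need to know whether events in a withdrawn patient still reach the CI.

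**Working it through.** **1. Trigger and consequence.** The trigger joins two different statements (leaving the trial; not contributing further data) with the word or. Both lead to the end of data collection. No intermediate level is described.

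**2. What can still be obtained after a patient leaves the assessments.**

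| Outcome | Source in the protocol | Obtainable without the patient? |
|---|---|---|
| Time to surgical fitness for discharge | ERP Database (5.4, 7.1) | Yes |
| Actual discharge, hence hospital stay | ERP Database (7.1) | Yes |
| Some morbidity (POMS) items | Source not stated; notes are a named general source (7.1) | Partly, by judgement |
| Adverse events | Patient notes (8.2) | Yes, if recorded there |
| HOMA, cortisol | Research blood samples (7.1, 10.2) | No |
| PQRS, VAS scores, grip strength | Patient contact | No |

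This assumes that the ERP Database and the notes are completed for every ERP patient, whether or not they remain in the trial. Being in the ERP is an inclusion criterion.

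**3. Set against intention to treat.** Section 7.3 wants all analyses by intention to treat. Section 9.3 stops collection of outcomes that would still exist for a randomised patient. The two can coexist formally, because the primary analysis uses the data obtained, but the second creates avoidable missing data for the first.

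**4. Set against safety reporting.** Section 8.2 runs from treatment to discharge with no exception for withdrawn patients. Section 9.3 ends collection with no exception for safety data. Recording in the clinical notes can continue in any case. What is unclear is whether the research team may still look for events and pass them to the CI, who reports causally attributed SAEs to the REC. The adverse-event outcome itself closes at the end of POD 1 (5.4, 7.1), so a later withdrawal affects the reporting duty rather than that comparison.

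**5. Size.** The plan's own figure comes first. Inputs from section 5.6: difference 15%, SD 16%, two-sided 0.05, power 80%, attrition 10%.

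- n per group = 2 × [16 × (1.960 + 0.8416) / 15]² = 17.86, so 18.
- 18 / 0.90 = 20 per group, as stated.
- Power with 18 analysed per group: 80.3% (normal approximation), 78.0% (exact t-test).

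These figures concern POD 1 HOMA. A patient who refuses sampling before POD 1 is missing for it under any withdrawal wording. One who withdraws after the POD 1 samples is already included, because earlier data are kept. The wording therefore leaves the primary analysis essentially unchanged. For the record-based outcomes, each patient lost is 1/20 = 5% of an arm. The protocol does not say how many to expect.

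**The case against.** The strongest reply is that ending all collection on explicit withdrawal is a coherent consent choice, since consent is described as covering intervention, assessments and data together, and that the clearly recoverable outcomes are few and secondary. Both observations are fair. They limit the importance of the point, but they do not explain why a patient willing to allow use of records should be given no way to do so.

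A reader might also infer several stronger things that the documents do not support:

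- **That declining any one part ends everything.** The trigger is an explicit statement of leaving the trial or contributing no more data. A patient who refuses one blood sample has said neither. Partial withdrawal is not addressed.
- **That asking to stop leads to erasure.** Destruction has its own trigger. Nothing says that clinical notes or reports already made to the CI or REC are destroyed. Whether the five-year retention in section 7.2 covers such a patient's documents is unstated, which is an ambiguity rather than a proven conflict.
- **That the adverse-event rules flatly contradict each other.** Section 8.2 concerns entries in the patient notes and excludes events due to the patient's condition, and section 9.4 gives no time window. This is a tension, because neither rule mentions the other.
- **That two patients per arm will be lost.** 10% of 20 is 2, but that is the whole attrition allowance, which may include lost samples and other kinds of withdrawal.
- **That the comparisons will lean in a known direction.** Selective loss is possible, but the rule is the same in both arms and patients are blinded. No direction can be read from the protocol.

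**Conclusion.** The point holds in a limited form. As written, the rule discards later record-based secondary outcomes, above all time to surgical fitness and discharge time, for a patient who leaves the assessments but would allow use of routine records. That sits badly with the intention-to-treat statement. The rule also leaves open whether reporting of adverse events to the CI continues after withdrawal.

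The size is 5% of an arm per such patient on those outcomes, with the number of patients unknown and no meaningful effect on the primary outcome. The conclusion rests on two assumptions: that the ERP Database and notes are kept for withdrawn patients as part of routine care, and that some patients who leave would agree to their records being used. The change is worth making because it is cheap and the lost data cannot be recovered afterwards.

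**What to change.** In section 9.3, the information sheet and the consent form, separate two requests: (i) stopping study assessments, meaning blood samples, questionnaires and grip tests; and (ii) refusing further use of routine records. Under (i), go on collecting outcomes from the ERP Database and the notes, and adverse events, to discharge unless the patient also chooses (ii). The drink is a single pre-operative dose, so a separate level for stopping it adds little.

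State in the same place how the adverse-event reporting duty applies after each kind of withdrawal. State also which records the destruction rule covers, with explicit mention of the consent form, the allocation record, the withdrawal date and adverse events already reported. Sections 7.2, 8.2, 9.3 and 9.4 should then be reconciled.

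The cost is wording and an REC amendment under section 9.2, plus a slightly longer conversation when a patient withdraws. No extra visits or staff are needed.
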